5.4 Screening and subject numbers

Each subject who has signed the ICF will be assigned a screening number and shall be listed on a subject screening and inclusion log. Each screened subject will be assigned a screening number consisting of “S” and the site number followed by a consecutive number starting with 01 at each site, e.g., S101, S102. The screening number shall be listed on a subject screening and inclusion log.

A “screening failure” is defined as a subject who does not fulfil the eligibility criteria. For screening failures, the eCRF screening visit shall be completed to an extent that makes it clear which assessments have been made and the reason why the subject did not fulfil the eligibility criteria. The reason for excluding a subject from entering the study shall also be specified in the subject screening and inclusion log.

When the Investigator has confirmed that all inclusion criteria and no exclusion criteria are met, each enrolled subject will be assigned a subject number by the eCRF consisting of the site number followed by a consecutive number starting with 01 at each site, e.g., 101, 102 etc.

The subject number, subject name, and other information sufficient to link the eCRF to the medical records (e.g., national identification number, chart number, etc.) shall be recorded on a subject identification list. The subject identification list shall only be available at the site, both throughout and after the study.

5.5 Withdrawal of subjects

Each subject shall be advised in the informed consent form that he/she has the right to withdraw from the study at any time, for any reason, without prejudice. Subjects may also be discontinued from this study if the Investigator determines that it is in the subject's best interest to do so, and may be withdrawn at the Investigator's discretion at any time.

The withdrawal criteria are:

- **Medical reasons:** If the subject suffers from a medical condition that in the judgment of the Investigator makes it medically necessary to withdraw the subject. The specific rationale for Investigator initiated withdrawal of a subject for medical reasons shall document the specific condition for withdrawing the subject.
- **Subject request:** Includes consent withdrawal, subject relocation, schedule conflicts. A subject can withdraw their consent to participate in the study at their own request or be withdrawn from participation in the study at the request of their legally authorized representative at any time for any reason.
- **Lost to follow-up:** If a subject does not return for a scheduled visit, reasonable effort shall be made to contact that subject, e.g., call three times at different hours and leave messages, if applicable, or confirm with two documented phone calls and a certified letter (delivery receipt requested) without answer, before declaring the subject lost to follow-up.
- **Other:** This category is to be used for a subject who discontinues due to a reason other than as specified in the pre-defined categories above, e.g., failure to comply with protocol requirements or to complete the protocol-specified evaluations.

 GALDERMA	Title 43CH1508 Clinical Study Protocol	Doc id MA-29708
--	---	----------------------------------

Effective date: 2017-07-05 06:37

Effective

Version: 5.0

The reason and date for withdrawal shall be documented in the eCRF. When possible, an explanatory comment shall be added in the study termination module/pages to further explain the reason for withdrawal. If withdrawal of a subject occurs during a regular study visit, the eCRF for that specific visit shall be completed as far as possible together with the study termination eCRF module and a final pregnancy test (U-HCG) will be done in women of childbearing potential.

If withdrawal of a subject occurs between regular study visits the subject should, when possible (irrespective of the reason for withdrawal), be scheduled for a termination visit. In these cases the eCRF for early termination visit should be completed.

If a subject is withdrawn from the study, all data collected until the time of withdrawal will be used in the analyses.

A withdrawn or discontinued subject must not be replaced or re-entered into the study.

If an AE which, according to the Investigator's assessment, is related to the use of any of the study products and is still ongoing at the time of the withdrawal please refer to Section [8.4.6](#).

6 STUDY PRODUCTS

The term "study products" refers to Restylane Defyne and Restylane. Both Restylane Defyne and Restylane will be supplied by the Sponsor.

6.1 Investigational product

Restylane Defyne (with lidocaine) is a sterilized injectable gel consisting of stabilized HA of non-animal origin with the addition of 3 mg lidocaine hydrochloride per mL. The product contains 20 mg/mL HA in a physiological phosphate buffer system. The gel is transparent and colorless. The product is supplied in a prefilled plastic syringe with a luer-lock fitting. Two 27G × ½" ultra-thin wall needles are packed together with each Restylane Defyne syringe. The syringe, containing 1 mL gel, is labeled and packaged in a blister. The investigational product is for single use only.

Commercial Restylane Defyne produced for the EU market will be provided to the sites and detailed product information is available in the IB and the instructions for use (IFU) ([Appendix 2](#)).

6.2 Reference product

Restylane is a sterilized injectable gel consisting of stabilized HA of non-animal origin with a concentration of 20 mg/mL in phosphate buffered saline. The gel is transparent and colorless. The product is supplied in single use glass syringe with a luer-lock fitting. Two 30G × ½" needles are packed together with each Restylane. The syringe, containing 1 mL gel, is labeled and packaged in a blister. The product is for single use only.

The reference product is commercial product intended for the Chinese market. An IFU is included in the carton and also available in [Appendix 3](#).

 GALDERMA	Title 43CH1508 Clinical Study Protocol	Doc id MA-29708
--	---	----------------------------------

6.3 Additional products and material

Restylane Defyne and Restylane, pre-packed in blister with two needles, will be supplied by the Sponsor.

Any other additional products required for the study, e.g., topical or local anaesthetic, pain relief, and adequate medical equipment in case of clinical emergency will be supplied by the Investigator.

6.4 Packaging, labelling, and storage

Restylane Defyne (with lidocaine) and Restylane (without lidocaine) are manufactured by Q-Med AB, Uppsala, Sweden, who will supply the study products. Restylane Defyne, the investigational product, is CE-marked, i.e., commercial product intended for the EU-market. The reference product, Restylane, is commercial product intended for the Chinese market. Commercial Restylane Defyne intended for the EU market and commercial Restylane intended for the Chinese market will be used in the study.

The syringes are labelled with name of the product and the name of the manufacturer (Q-Med AB). The syringes in its blister are packed in a carton. The carton will be labelled in local language, specifying the Sponsor name, protocol number, lot number, expiry date and that the product is to be used for clinical studies exclusively.

The study products should be stored at a temperature up to 25°C and protected from sunlight and freezing. Opened syringes should not be re-used. The expiry date is indicated on package.

6.5 Product accountability

The study products will be released to the PI or his/her authorized designee after study approvals have been received from the IEC and other relevant authorities/institutions, as applicable, and the CTA has been signed by all parties.

The PI must ensure that the study products are kept in a secure location, with access limited to those authorized by the PI.

The study products must be traceable from the manufacturer(s) to their use in subjects until return or disposal. It is therefore important that the PI maintains accurate product accountability records, i.e., documentation of the physical location of all study products, deliveries, and return of study products between the Sponsor and the PI, and documentation of administration of product to the subject. A shipping record shall be kept of all study products received from the Sponsor; including the product name, date received, lot number, expiration date, and amount received. In addition, dispensing logs shall be maintained including the product name, dispense date, the number of syringes used/amount dispensed, the subject receiving study product, and number of syringes left in stock at the site. A log for accountability procedure is provided by the Sponsor.

When the study is completed, all unused or expired study product at each study site shall be returned to the Sponsor or a third-party vendor for destruction or be destroyed locally at the site, with proper documentation, after agreement with the Sponsor. Any malfunctioning study products shall be reported as described in Section 8.5.3.

 GALDERMA	Title 43CH1508 Clinical Study Protocol	Doc id MA-29708
--	---	----------------------------------

Products deliberately or accidentally destroyed during shipment or at a study site shall be accounted for and documented. Used syringes, disposable needle and any opened unused material must be discarded immediately after the treatment session and must not be reused due to risk for contamination of the unused material and the associated risks including infections according to standard procedures at the site. Disposal of hazardous material, i.e., syringes and needles must conform to applicable laws and regulations. The study products must not be used outside the study.

6.6 Treatment

6.6.1 Treatment procedure

The subjects will be informed about the indications, expected result, precautions, and potential AEs.

Injection procedures are associated with a risk of infection. Aseptic technique and standard practice to prevent cross-infections should be observed at all times including the use of disposable gloves during the injection procedure. The subject should not wear make-up on the day of treatment, if make-up was already applied this must be completely removed prior to any injection. The treatment site should be thoroughly cleaned at least twice with a suitable antiseptic solution.

The treating Investigator will confirm randomization *via* the eCRF system for study products i.e., the NLF on one side of the face will be randomly assigned to treatment with Restylane Defyne and the opposite NLF to treatment with Restylane. Treatment will always start in the subject's right NLF. Restylane Defyne should be injected into the mid to deep dermis of the facial skin in the NLF and Restylane should be injected into the middle part of the dermis layer of the facial skin in the NLF.

The treating Investigator should keep the subject blind to the treatment by placing an opaque drape or patch over the subject's eyes during the time that the injections are administered. The details regarding randomization and blinding of subjects and blinded evaluator are in Section 4.4.

To avoid breakage of the needle, no attempt to bend or otherwise manipulate the needle before or during treatment is recommended. Before injecting, the air should be removed by pressing the rod carefully until a small droplet is visible at the tip of the needle. Aspiration prior to injection in order to avoid accidental intravascular injection is recommended. The linear threading technique can be used to carefully lift up the wrinkle. The injection technique should be the same for both sides of the face in any one subject to limit variability due to technique. Both products should be injected slowly while pulling the needle backwards. Injection should stop just before the needle is pulled out from the skin to prevent material from leaking out from the injection site. Excessive pressure must not be applied at any time during injection. If resistance is encountered the needle should be partially withdrawn and repositioned or fully withdrawn and checked for function. Separate sterile needles should be used for each NLF. The injection sites may be gently massaged **CCI** [REDACTED] by the treating Investigator to conform the contour of the surrounding tissue.

At the initial treatment visit (Day 1) subjects should assess the pain experienced during treatment. **CCI** [REDACTED]

In order to be able to

 GALDERMA	Title 43CH1508 Clinical Study Protocol	Doc id MA-29708
--	---	----------------------------------

evaluate the pain of injection, separated from the pain of the needle insertion alone, a pause of 3 to 5 second is required after insertion of the needle before starting the injection. Both products should be injected slowly as injection pace could affect the pain experienced; the time required for each injection will be recorded in the eCRF. **CCI**

The injection procedure for the two NLFs will be standardized as far as possible in terms of volume, time required for injection, depth of injection, and injection technique and will be recorded in the eCRF.

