--	--

 GALDERMA	Title 43CH1508 Clinical Study Protocol	Doc id MA-29708
Investigational product, dose and mode of administration:	
Restylane Defyne (with lidocaine) consists of stabilized hyaluronic acid of non-animal origin at a concentration of 20 mg/mL in phosphate buffered saline with lidocaine hydrochloride 3 mg/mL. The study product is supplied in sterile 1 mL syringes. A 27G × ½" ultra-thin wall needle will be used for injection.
 
The treating Investigator will check the randomization via the eCRF system for study product, i.e., the NLF on one side of the face will be randomly assigned to treatment with Restylane Defyne and the opposite NLF to treatment with Restylane.
 
Restylane Defyne should be injected into the mid to deep dermis of the facial skin in the NLF. The injection procedure should strictly follow the rules of aseptic surgical technique (refer to the Restylane Defyne Instructions For Use for details).
 
For initial treatment, it is recommended not to use more than 1.5 mL for each NLF. For touch up treatment, it is recommended not to use more than 0.5 mL for each NLF.
 
The linear threading technique can be used to carefully lift up the wrinkle. The injection technique should be the same for both sides of the face in any one subject to limit variability due to technique. Sufficient amounts of product should be injected to fully correct the defect. Defects should be fully corrected, but not overcorrected
 
CC1
 
Restylane Defyne is approved under the brand name Emervel Deep Lidocaine in several countries.
	

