4.4.2 Blinding

Due to the differences in the physical characteristics (viscosity) of the study products and the difference in syringe design and material (size of syringe and plastic *vs* glass syringe), it is not possible to truly double-blind the study, and the treatment assignment cannot be obscured from the treating Investigator.

Because the method of administration is similar, the treatment can be masked from the subjects by simply preventing them from viewing the syringes during administration of the study products. This will be done by placing an opaque drape or patch over the subject's eyes during the injection procedure.

The blinded evaluator shall not be allowed to retrieve study supplies or to be present during opening of the study supplies or injections. The treating Investigator is not allowed to discuss treatments with the blinded evaluator or the subjects. All documents with information on study products shall be kept in a separate binder not available to the blinded evaluator. The blinded evaluator should not have access to eCRF pages with study product information.

The Sponsor and the Sponsor's representative at the site shall not be blinded during the study.

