- Do not inject intravascularly. As for other injectable medical devices, inadvertent injection into or next to blood vessels could potentially lead to vascular occlusion or compression, ischemia and necrosis.
- Do not use in patients with bleeding disorders or in patients who are taking thrombolytics or anticoagulants.
- Do not inject this product into an area where an implant other than hyaluronic acid has been placed.
- Do not resterilize.
- Do not mix with other products.

VII. PRECAUTIONS FOR USE

General considerations relevant to injectable medical devices

- Knowledge of the anatomy of treatment site and special caution are required in order to avoid perforation or compression of vessels, nerves and other vulnerable structures.
- Injection procedures are associated with a risk of infection. Aseptic technique and standard practice to prevent cross-infections are to be observed.
- Special caution should be exercised when treating areas with limited collateral circulation, due to increased risk of ischemia.
- Special caution should be exercised in treating facial areas with limited soft tissue support or soft tissue cover, such as the periorbital area, to avoid formation of palpable lumps.
- Patients with pre-existing pigmented dark lower eye lid circles, thin skin and pre-existing tendency toward oedema formation are not suitable candidates for treatment of the lower periorbital region.
- Patients using immunosuppressants are not suitable candidates for treatment.
- Special caution should be exercised in treating patients with a tendency to form hypertrophic scars or any other healing disorders.
- Injection procedures can lead to reactivation of latent or subclinical herpes viral infections.
- Patients who are using substances that affect platelet function, such as aspirin and nonsteroidal anti-inflammatory drugs may, as with any injection, experience increased bruising or bleeding at injection sites.
- Patients with unattainable expectations are not suitable candidates for treatment.
- Do not use the product if the package is damaged.

 GALDERMA	Title 43CH1508 Clinical Study Protocol	Doc id MA-29708
--	---	----------------------------------

- Do not use the product if the contents of the syringe are cloudy.

Specific considerations relevant to the use of this product

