Injection related adverse events such as bruising, erythema, itching, swelling, pain and tenderness generally resolve spontaneously within one week after injection.

Vascular compromise may occur due to an inadvertent intravascular injection or as a result of vascular compression associated with implantation of any injectable product. This may manifest as ischemia or necrosis at the implant site or in the area supplied by the blood

 GALDERMA	Title 43CH1508 Clinical Study Protocol	Doc id MA-29708
--	---	----------------------------------

Effective date: 2017-07-05 06:37

Effective

Version: 5.0

vessels affected; or rarely as ischemic events in other organs due to embolisation. Following facial aesthetic treatments isolated rare cases have been reported regarding ischemic events affecting the eye leading to visual loss, and the brain resulting in cerebral infarction. After injections of the nose ischemia/necrosis may occur, especially in patients who had prior rhinoplasty.

Symptoms of inflammation at the implant site commencing either shortly after injection or after a delay of up to several weeks have been reported. In case of unexplained inflammatory reactions infections should be excluded and treated if necessary since inadequately treated infections may progress into complications such as abscess formation. Treatment using only oral corticosteroids without concurrent antibiotic treatment is not recommended. In case of persistent or recurrent inflammatory symptoms, consider removal of the product by aspiration/drainage, extrusion or enzymatic degradation (use of hyaluronidase has been described in scientific publications). Before any removal procedure is performed, the swelling may be reduced by using e.g., NSAID for 2-7 days or a short course of corticosteroids for less than 7 days, in order to more easily palpate any remaining product.

For patients who have experienced medically important adverse events, a decision for retreatment should take into consideration the cause and severity of previous reactions.

For reporting adverse events contact your local Galderma representative or distributor for this product.

IX. PERFORMANCE

In a randomized controlled multicenter study with Restylane Defyne for correction of moderate to severe nasolabial folds, 69.8% of subjects maintained a clinically significant improvement at 48 weeks after treatment.

X. TREATMENT PROCEDURE

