Inform the patient about the precautions to be taken, the expected result and the possible adverse events.

It is important to use a sterile, appropriate needle or blunt cannula. Suitable needles (27G x $\frac{1}{2}$ " Ultra thin wall) are supplied with the syringe in the blister pack. As an alternative, a blunt thin walled cannula with a recommended size of 27G can be used.

Assembling the needle/cannula and syringe:

- use surgical gloves
- unscrew the protective cap from the stopper
- carefully remove the stopper from the syringe
- firmly screw the needle/cannula with its shield onto the tip of the syringe
- remove the shield just before injection

Cleanse the area to be treated with an antiseptic and allow it to dry before injection.

To avoid breakage of the needle/cannula, do not attempt to bend or otherwise manipulate it before or during treatment.

 GALDERMA	Title 43CH1508 Clinical Study Protocol	Doc id MA-29708
--	---	----------------------------------

Effective date: 2017-07-05 06:37

Before injecting the product, depress the plunger rod carefully until a small droplet is visible at the tip of the needle/cannula.

Align the bevel of the needle by turning the syringe on its axis. If a blunt cannula is used, an entry point is made in the skin, for example with a sharp needle of appropriate size.

Aspiration is recommended prior to injection in order to reduce the risk of inadvertent injection into a blood vessel. Inject slowly. During injection, keep the side hole of the cannula facing downwards, away from the skin surface.

Inject the gel by gently pressing down on the plunger rod with the thumb or palm of the hand. Choose from a variety of injection techniques, i.e., serial puncture, linear threading or cross-hatching.

It is recommended to change needle/cannula for each new treatment site.

Defects should be fully corrected, but not overcorrected, at each treatment session.

If "blanching" of the skin is observed as a result of over-superficial injection, the whitened area should be massaged gently until it returns to a normal colour.

Gently massage the treated area after injection.

The syringes and needles/cannulas must be discarded immediately after use in accordance with accepted medical practice and applicable national, local or institutional guidelines. The product shall not be reused due to risk for contamination of unused material and the associated risk including infection.

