- To help avoid needle breakage, do not attempt to straighten a bent needle. Discard it and complete the procedure with a replacement needle.
- Do not reshield used needles. Recapping by hand is a hazardous practice and should be avoided.
- Discard unshielded needles in approved sharps collectors.

Contraindications

1. 瑞蓝 2 (Restylane) is contraindicated for patients with severe allergies manifested by a history of anaphylaxis, or history or presence of multiple severe allergies.
2. Do not use in patients with a history of hypersensitivity to streptococcal proteins, as the product may contain trace amounts of such material.
3. 瑞蓝 2 (Restylane) should not be used in the following situations:
 - Permanent implant or implant other than hyaluronic acid in the same area
 - Non-permanent implant placed in the same area during the previous 6-12 months
 - If no information is available on the type of implant
4. Do not use in patients with bleeding disorders or patients who are taking thrombolytics or anticoagulants.
5. Do not use where there is active disease, such as inflammation, infection or tumours, in or near the intended treatment site.

Warnings

1. 瑞蓝 2 (Restylane) is only intended for use as an intradermal implant. The product should not be used for breast site injections.
2. Do not resterilize 瑞蓝 2 (Restylane).
3. Do not inject intramuscularly or intravascularly. Aspiration prior to injection is recommended.
4. Unintentional introduction of soft tissue fillers into the vasculature in the face may lead to embolization, occlusion of the vessels, ischemia, necrosis or infarction at the implant site or in the area supplied by the blood vessels affected. Rare but serious adverse events include temporary or permanent vision impairment, blindness, cerebral ischemia or stroke. Stop the injection immediately if blanching occurs or if a patient complains of unusual pain or exhibits any symptoms suggestive of inadvertent intravascular injection. Such patients should receive prompt medical evaluation and attention.
5. 瑞蓝 2 (Restylane) should not be mixed with other products before implantation of the device.
6. The product is for single use only.
7. Do not use if package is damaged.

 GALDERMA	Title 43CH1508 Clinical Study Protocol	Doc id MA-29708
--	---	----------------------------------

Precautions

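### Covering the subject's eyes during injection hides one warning sign, loss of vision, that the appended stop rule relies on; the added risk is very small and the fix is cheap.

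*Protocol*

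**What the plan says.** Protocol 4.4.2 reasons that "the treatment can be masked from the subjects by simply preventing them from viewing the syringes during administration", and continues: "This will be done by placing an opaque drape or patch over the subject's eyes during the injection procedure". Section 6.6.1 repeats this as a treatment step: "The treating Investigator should keep the subject blind to the treatment by placing an opaque drape or patch over the subject's eyes". No purpose other than hiding the syringes is given. The masking has a visible use, because 6.6.1 has subjects rate injection pain on Day 1.

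Both IFUs appended to the protocol recognise the hazard:

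- **Appendix 2 (Restylane Defyne)** warns that "inadvertent injection into or next to blood vessels could potentially lead to vascular occlusion or compression, ischemia and necrosis". Under adverse events it reports isolated rare cases of "ischemic events affecting the eye leading to visual loss, and the brain resulting in cerebral infarction".
- **Appendix 3 (Restylane, China)** names temporary or permanent vision impairment and blindness after filler enters facial vessels. It then instructs: "Stop the injection immediately if blanching occurs or if a patient complains of unusual pain or exhibits any symptoms suggestive of inadvertent intravascular injection".

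Other precautions are already in the plan. The synopsis says aspiration should be performed, and 6.6.1 recommends it. Section 6.6.1 also calls for slow injection without excessive pressure and has subjects told of potential adverse events. Section 6.3 has the investigator supply emergency medical equipment. Sections 4.8.2 and 4.8.3 list an adverse event evaluation after treatment.

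**The concern.** Appendix 3 relies partly on what the patient can report, and loss of vision is one of the outcomes it names just before the stop instruction. An opaque cover removes that report while it is in place. If filler enters a vessel that supplies the eye and the first or only sign is visual, the injector gets no signal and may go on injecting. The recommended maximum is 1.5 mL per fold at initial treatment and 0.5 mL at touch-up. The harm could be irreversible, in an elective cosmetic procedure, and the obstacle comes from the masking method rather than from the treatment. This is a question of subject safety only; the primary endpoint and its analysis are not affected.

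**Working it through.** **Step 1: which warning signs survive the cover.** This follows from reading 4.4.2 and 6.6.1 against Appendix 3.

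| Sign | Detectable with the eyes covered? |
|---|---|
| Blanching | Yes, seen by the injector |
| Unusual pain | Yes, reported by the subject |
| Non-visual symptoms | Yes |
| Loss of vision | No, until the cover is lifted |

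Aspiration and slow injection lower the chance of an event, and emergency equipment helps afterwards. None of them restores the visual signal during the injection.

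**Step 2: how long the signal is hidden.** If the cover comes off after each fold, a symptom that begins mid-injection is delayed by the remainder of that fold. If it stays on for both folds, the delay is longer. The visible text does not say which applies. In 4.8.2 an item between the right-fold and left-fold treatments is redacted, and it may already involve uncovering. In 4.8.3 the touch-up is listed as one treatment step with no visible item between folds. The documents give no injection time. It is recorded at initial treatment only (Protocol 6.6.5) and will be summarised in minutes (SAP 2.3.5, Table 7-3).

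**Step 3: how often a visual event might occur.** The protocol gives no figure for this, so there is none to reproduce.

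- Number of subjects: n = 175 (Protocol 4.2).
- Rate: r = 1/100 000 to 1/10 000. This is the Appendix 3 post-marketing reporting band for visual disturbances, per estimated Restylane treatment.
- Assumption: the band applies once per subject to a split-face treatment that includes Defyne. The documents give no visual-event rate for Defyne.
- Formulas: expected reports = n × r; P(at least one) = 1 − (1 − r)^n.

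| r | Expected reports | P(at least one) |
|---|---|---|
| 1/100 000 | 175 × 0.00001 = 0.00175 | 1 − 0.99999^175 = 0.17% (about 1 in 572) |
| 1/10 000 | 175 × 0.0001 = 0.0175 | 1 − 0.9999^175 = 1.7% (about 1 in 58) |

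The count depends on what one treatment means. Counting each fold (2 × 175 = 350) gives 0.35% to 3.4%. If every fold also had a touch-up (2 × 350 = 700), the range is 0.70% to 6.8%.

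**Step 4: from any visual report to a hidden event.** The Appendix 3 category includes transient blurred vision, drooping eyelid and tearing, so the figures overstate the chance of blindness. Only events that begin during injection, with vision as the only sign, would be hidden. The documents do not give that share, so the lower limit is zero.

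**The case against.** The strongest case on the other side is that this is a deliberate masking choice serving the pain rating, for an event so rare that the trial will probably never see one. The increment due to the cover cannot be quantified. Appendix 3 requires Restylane injectors to be trained and certified. Both IFUs bear on every planned initial session, because each subject receives both products. Most warning signs are untouched, and the redacted Day 1 item may already provide a check between folds. Nearly all of this stands, and it is why the point is minor. It does not answer the narrow point: training cannot recover a symptom the subject cannot perceive, and a check between folds does not help during the injection itself.

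A reader might infer three stronger things that the documents do not support.

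- *That the Defyne IFU tells the injector to massage over a suspected vessel occlusion.* The Appendix 2 advice that "the whitened area should be massaged gently until it returns to a normal colour" is limited to blanching caused by injecting too superficially. Appendix 3 also mentions massage, after stopping.
- *That no stop rule covers the Defyne fold.* The synopsis does send the Defyne injector to that product's own IFU ("refer to the Restylane Defyne Instructions For Use for details"), and the Appendix 2 text contains no stop-on-symptom instruction. But Appendix 2 is labelled an extract, and the Appendix 3 warning is worded for soft tissue fillers in general. What is left is a missing cross-reference in the visible text of 6.6.1.
- *That vision is never checked between folds.* Redactions in 4.8.2 and 6.6.1 rule out that conclusion.

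**Conclusion.** As written, the masking disables one of the signals behind the Appendix 3 stop rule for as long as the cover is on. That follows directly from the text. The size is very small. The chance of any visual report across 175 treatments is about 0.2% to 1.7%, of which an unknown and possibly zero share would be hidden. This rests on applying the Restylane band once per subject, Defyne included, and on taking reporting frequencies at face value. It would be wrong to read 1.7% as the risk of hidden blindness. The case for change rests on potentially irreversible harm set against a very low cost, so this is a cheap, minor improvement.

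**What to change.** Put the same text in both 6.6.1 and 4.4.2, so that the two sections do not conflict, and apply it to initial treatment and touch-up:

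> Cover the eyes only while a fold is being injected. After each fold, put the syringe out of view, uncover the eyes, ask about vision and look at skin colour. If either is abnormal, do not start or continue injection and obtain prompt medical evaluation. For both products, stop the injection immediately on blanching, unusual pain or any visual or neurological symptom.

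A screen that hides the syringe without covering the eyes can be optional where a site finds it practicable. Uncovering after each fold shortens the hidden period; only a screen removes it.

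The cost is a wording amendment and a site letter, a short pause per fold, and care to keep the syringes out of view so that the Day 1 pain rating stays masked. No extra staff are needed, and visits, endpoints and analysis are unchanged. If the redacted Day 1 step already uncovers the eyes, that part only confirms existing practice.
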